Rationale: Inborn Errors of Metabolism (IEM) are monogenic conditions in which the impairment of a biochemical pathway is intrinsic to the pathophysiology of the disease. Organ dysfunction results from intoxication and/or storage of metabolites, as well as a shortage of energy and building blocks. Rapid diagnosis of IEM enables initiation of targeted treatment (e.g. diet) slowing down or stopping the degenerative nature of the disease, resulting in significantly reduction of morbidity and mortality. A diagnosis also enables prognostication, access to community services and accurate genetic counselling for the patient and his/her family. Diagnosing IEM can be a major challenge, because of phenotypic heterogeneity and complex, expensive, diagnostic tests. Whole exome/ genome sequencing (WES/WGS) has revolutionized diagnostics of rare diseases and IEM, but still gives a negative or inconclusive result in >50% of cases. Addition of other omics technologies (metabolomics, glycomics, lipidomics, epigenomics, transcriptomics, proteomics) with integrated bioinformatics increases diagnostic yield, as it may point to the defective pathway allowing scrutinizing genes in genomic data or vice versa: it generates evidence of the deleterious functional impact of a DNA variants of unknown significance (VUS). In this study we will unite our national expertises and apply a multi-omics approach to solve the unsolved genetic basis of patients with a metabolic phenotype on a larger scale.

Objective: Integrating genomic (WES/WGS) and other -omics technologies in order to find the genetic causes, in 500 patients (children and adults) with an unexplained metabolic phenotype in whom standard care (genetic and metabolic evaluation) did not provide a diagnosis.

Study design: A prospective, diagnostic (deep phenotyping, WES/WGS and pan-omics) multicenter cohort study.

Study population: (In)capacitated patients (all ages/both genders) with a clinical (and/or family) history and abnormal additional examination (physical (neurological)/ biochemical/ radiological/ genetic) suspicious for an IEM, without diagnosis.

Main study parameters/endpoints: 1) identification of a genetic variant and alignment with its biochemical and phenotypical abnormalities; 2) evaluating the diagnostic yield of combined WES/WGS and omics techniques

Methods used: Patients with unexplained metabolic phenotypes are referred (on paper) and discussed by the ZOEMBA (Zoektocht naar Erfelijke MetaBole Aandoening) team. Clinical phenotyping, bioinformatic reanalysis of WES data and additional metabolomics will be performed in all participants. In case still no diagnosis is made, a tailormade diagnostic plan is made combining deep WES, WGS, glycomics, lipidomics, epigenomics, transcriptomics and/or proteomics leading to: a known IEM, a candidate variant or no diagnosis. In case of a

variant, additional functional studies (enzymatic assays, targeted omics, CRISPR/CAS, cell lines) will be performed to confirm the effect of the genetic variant on protein function. When still no diagnosis is established, matchmaking (genetic/phenotypical) through international databases might lead to a diagnosis.

Nature and extent of the burden and risks associated with participation, benefit and group relatedness:

The study involves collection of clinical data, reanalysis of previously analysed genetic data, additional “omics” and functional testing. All participants will have between 1 and 3 clinical visits for this study (at the UMC of referral) and a maximum of 2 telephone appointments with the arts-onderzoeker. Whenever possible study visits will be combined with regular hospital visits. Clinical data (clinical history, family history, physical examination, consultations, additional laboratory and/or radiological investigations) will be collected. A physical examination and blood and urine sampling will be performed in all participants at their first study visit. Any other already available biological samples (eg stored cell lines, dried blood spots, cerebrospinal fluid (CSF)) will be collected for re-analysis. For a selection of patients a skin biopsy will be performed at the 2nd clinical study visit for the use of functional studies. Potential burdens for participants are: the additional study visit(s), diagnostic procedures (e.g. blood, urine sampling and skin biopsy), as well as renewed (false) hope/uncertainty about finding a diagnosis. The potential benefit for all participants include: the opportunity to establish a diagnosis providing information on prognosis, (refinement of) management, genetic counselling with precise recurrence risk and option(s) for prenatal diagnosis.

1. Introduction and Rationale

Background: Rare Diseases (RD) and Inborn Errors of Metabolism (IEM)

The more than 7000 known rare genetic diseases collectively affect over 1,4 million persons in the Netherlands. The statistics on RDs are devastating: two-thirds of RDs are serious and disabling, three-quarters manifest in childhood, over half are life-limiting, most have no treatment and almost all have an enormous negative impact on family well-being (Boycott et al., 2013). Clearly, RDs represent a major healthcare challenge, contributing significantly to morbidity, mortality, and Dutch healthcare costs.

With the introduction of whole exome sequencing (WES), the targeted interrogation of the protein-coding exons (20,000 genes) of the genome in 2010, the identification of genes for many RD's, that were previously intractable to conventional gene discovery approaches, was facilitated. The diagnostic yield of WES has been shown to range from 25-30% in several large studies comprising ~5,000 patients (Lee et al., 2014; Yang et al., 2014; Retterer et al., 2016). Although very high compared to other tests, this clinical sensitivity still leaves >50% of patients with suspected genetic RDs without a conclusive diagnosis.

The focus of this study is to diagnose RD's caused by IEM presenting with systemic and/or neurologic findings. Inborn Errors of Metabolism (IEM) are monogenic conditions in which the impairment of a biochemical pathway is intrinsic to the pathophysiology of the disease. Intoxication and/or storage of metabolites with organ degeneration may be the result, as well as a shortage of energy and building blocks. More than 1000 IEMs are known, the genetic basis for many RD's remains to be discovered (Ferreira et al, 2018). In contrast to most rare genetic diseases with a degenerative phenotype, rapid diagnosis of IEM enables initiation of targeted treatment (e.g. diet, co-factor/vitamin supplements, substrate inhibition, enzyme replacement or stem cell transplantation) slowing down or stopping the degenerative nature of the disease, resulting in significantly reduction of morbidity and mortality (Coene et al., 2018; Graham et al., 2018; Horvath et al., 2018; [name] et al., 2016; [name] et al., 2016; Tarailo-Graovac et al., 2016). In addition, a diagnosis enables prognostication, access to community services and accurate genetic counselling for the patient and his/her family including prenatal options such as Preimplantation Genetic Diagnostics (PGD). Diagnosing patients with an IEM can be a major challenge, because of phenotypic heterogeneity and complex diagnostic tests. As a result, individuals suffering from IEM undergo very long and expensive diagnostic trajectories (often over a decade) and suffer health loss that may be prevented or ameliorated by timely diagnosis.

Current diagnostic trajectories of patients suspected of having an IEM

In general, symptoms of patients with an IEM are heterogeneous, affecting one or multiple organ systems and are often progressive in nature. Patients can have neurological (repeated rhabdomyolysis, exercise intolerance, neuropathy, myopathy, ataxia), ophthalmological (retinitis pigmentosa (RP)), otological (hearing loss and/or deafness) and/or endocrine abnormalities (hypoparathyroidism, hypoglycemia) as consequence of energy deficiency. In other IEMs endogenous intoxication causes neurological signs (encephalopathy, regression, movement disorder, psychiatric symptoms), ophthalmological (lens luxation) or organic abnormalities (liver and kidney function abnormalities. Storage associated IEMs, caused by enzyme deficiencies, can lead to yet different neurological (regression, psychiatric symptoms), ophthalmological (cataract/corneal clouding) and organ abnormalities (hepatosplenomegaly, cardiac hypertrophy, skeletal abnormalities, short stature, coarse facial features, umbilical/inguinal hernia). Many of the above mentioned features are disabling. Patients and family members hope to find therapies. They are often worried about the risk of recurrence of the disorder and future prospects. Without an accurate genetic diagnosis, these worries and questions cannot be addressed.

In current daily practice, patients with an unexplained metabolic phenotype, as outlined above, are seen by different medical specialists (e.g. ophthalmologists, endocrinologists, psychiatrists, neurologists, paediatricians, clinical geneticists). There is no standardized diagnostic evaluation of these patients; the presentation at the first specialist often determines the order in which diagnostic tests take place, which can vary from an eye examination, a cerebral MRI scan, cytogenetics to an exome or metabolomic testing.

Commonly, there are 2 main diagnostic trajectories that can be applied:

- 1) *targeted metabolic screening in plasma, urine and/or cerebral spinal fluid (CSF).*

When an abnormal metabolite pattern is identified, fitting with a known IEM, targeted DNA diagnostics are performed, to confirm the clinical diagnosis.

- 2) *targeted genetic testing through Sanger sequencing (in case of a strong clinical suspicion), gene panels consisting of several genes associated with a certain phenotype (e.g. movement disorder), targeted exome sequencing (exome-based panels) or true open trio-WES analysis (often analysis of the clinome which comprises all genes published associated with a human disease, correlating the variants found in the affected person to his/her parents to identify Mendelian disorders).*

There are several potential outcomes of this trajectory:

- 1) A known pathogenic IEM profile or mutation in a gene previously reported to cause a an IEM, fitting with the patient's features leading to a diagnosis.
- 2) In the remaining 50% (or more) no etiologic diagnosis is established, with two possible scenarios:
 - A DNA variant of unknown significance (VUS) in the WES and/or a metabolic alteration in metabolic investigations is/are identified, which cannot be unified into a confirmed diagnosis.
 - No clues arise from (both) the above mentioned diagnostic trajectories

Causes for inconclusive results in undiagnosed patients with metabolic phenotypes

The reasons why a patient remains undiagnosed is that certain phenomena are not being picked up by the current standard test used in clinical care. Using WES it is known that certain types of genetic alterations (e.g. repeat expansions, mutations in the mitochondrial DNA, intronic mutations) are not identified. In addition, some parts of some genes have low coverage (for instance due to CG-enriched genes or mosaicism) (Pena et al., 2018; Zeiger et al., 2018). Metabolic analysis is based on a broad set of screening tests. In these tests not all metabolites are detected. Untargeted Metabolomics is relatively new and has not been implemented in clinical care settings.

With the combined approach to **identify** potential disease-causing DNA variants and **functional validation** of these variants to support their pathogenicity (e.g., data sharing and biological studies) new IEM's are elucidated, paving the way for (future) treatment options and genetic counseling. The success of the combined application of exome sequencing and extended metabolic analysis with omics technologies (metabolomics, glycomics, lipidomics, epigenomics, transcriptomics, proteomics) has recently been shown in several studies (Haijes et al., 2019; Coene et al., 2018; Graham et al., 2018; Horvath et al., 2018; [name] et al., 2016; [name] et al., 2016; Tarailo-Graovac et al., 2016).

New diagnostic possibilities for undiagnosed patients with metabolic phenotypes

To increase the diagnostic yield in patients with an unexplained metabolic phenotype, the following approaches can be used:

- 1) *Reanalysis of exome sequencing data.* There is now emerging data to suggest that re-analysis of exomes initially reported as negative is of significant diagnostic value. As this reanalysis takes time and resources, not currently available in daily clinical care, currently reanalysis is mostly done on research base. A recent study described 10% diagnostic yield of re-analysis of 40 clinical exome analyses, 1-3 years after the original report (Wenger et al., 2017).

In addition, analysis of data in a research setting allows for novel gene discovery, potentially doubling the solve rate (Beaulieu et al., 2014; Eldomery et al., 2017). A cohort analysis of undiagnosed patients with similar biochemical features, suspected of having an IEM, might reveal rare variants in the same gene in different patients which would be missed when sequencing data were analysed on a patient-by-patient basis (Massink et al., 2015; van Hasselt et al., 2014).

- 2) *Deep sequencing*. Typically, laboratories using next-generation sequencing technologies strive to cover each base of DNA with an average of 100 reads. Recent studies have shown, however, that additional read depth coverage (500x vs 100x) can aid in the identification of somatic mosaicism (mutations that are only present in a subset of cells) as a cause of a RD (Qin et al., 2015).
- 3) *Whole Genome Sequencing (WGS)*. This targets the entire genome, providing more complete coverage compared to exome sequencing, while significantly outperforming with respect to other types of genomic variation such as insertions/deletions, copy number variants, chromosomal rearrangements, or causative variants in regulatory regions. It is therefore not surprising that WGS has been shown to increase the diagnostic and discovery yield from 15 to 40% in several cohorts (e.g., Gilissen et al., 2014; Taylor et al., 2015; Carss et al., 2017).
- 4) *RNA-sequencing*. Certain genetic mutations, such as non-coding variants, are not readily assessed by genome wide sequencing. Recently, RNA sequencing (RNAseq) has been identified as an innovative technology with the power to assess the functional impact (pathogenicity) of noncoding variants on genome-wide basis (Pauli et al. 2018). Moreover, Kremer et al., 2018, showed how systematic "transcriptomics" via RNA seq lead to a molecular diagnosis in 10-35% of patients in whom WES failed to do so. There has also been an increased appreciation for the importance of mRNA splicing for human health; estimates suggest that splicing defects account for approximately 15% of genetic diseases (Krawczak et al. 1992). In line with this, recent studies in our lab using patient-derived dermal fibroblasts indicated that RNA-seq analysis of these cells has the power to reveal splicing defects such as lost splice junctions and retained intronic sequences resulting from pathogenic variants affecting the spliceosome machinery (manuscript in revision).
- 5) *Metabolomics*. Metabolomics allows for simultaneous profiling of thousands of metabolites and can pinpoint specific proteins in a pathway/biological process as candidates for disease causation (Graham et al., 2018).
- 6) *Glycomics*. In addition to metabolomics, glycomics provides complementary functional information on the consequences of potential disease mutations. In recent years, a wide variety of disease processes has been associated with abnormal

protein glycosylation, including ion homeostasis, Golgi trafficking and intracellular pH (Abu Bakar et al., 2018; Ashikov et al., 2018). In case of identifying disease mutations in such genes or related pathways, together accounting for >1000 genes, glycomics analyses can be performed.

- 7) *Lipidomics*. Lipidomics aims at the holistic characterization of lipid metabolism, predominantly by using high resolution mass spectrometry to perform semi-targeted identification of more than 1200 lipid species from many lipid classes. This technique has already been successfully applied to identify biomarkers/mechanisms in inborn errors of metabolism and is ideally suited to characterize disorders involving complex lipid metabolism (Herzog et al., 2016; Herzog et al., 2018; Herzog et al., 2018).
- 8) *Epigenomics*: Epigenetics is modification of DNA that does not alter its base sequence, but alters its expression and thereby alters phenotype (Jaenisch et al., 2003). With the introduction of whole epigenome analysis technology it had become feasible to look for aberrant DNA methylation patterns in patients that lead to mutations in underlying genes (Meeks et al., 2018). SOTOS syndrome (NSD1 mutations) for instance, is a classic example. It is known that especially in RD's associated with ID (Intellectual Deficits) genes associated with chromatin state are very much enriched. Since in many patients with RD (and ID) no genetic cause of their disease has yet been identified, epigenetic changes might well be involved. As an example, within the Amsterdam UMC, location AMC, we have recently discovered a new syndrome that is caused by mutation within the SETDB1 gene, demonstrating a classical recognizable DNA methylation pattern (article in progress Mannens et al.).

One challenging problem in diagnostics is the classification of DNA variants. Are these variants disease causing or merely harmless DNA variants? Studying the effect of DNA variants in epi-enzymes (proteins associated with the assembly of the chromatin structure) with whole epigenome technology discriminates between pathogenic variants and harmless DNA variants. This technology therefore serves not only as a new diagnostic test but also as a very valuable functional test. The genome diagnostics laboratory Amsterdam UMC (AMC) has recently set up this technology included an analysis pipeline as one of the first laboratories worldwide.

- 9) *Proteomics*. Other omics approaches have been developed that can aid RD discovery by pointing to a particular pathway or biological process for further interrogation.

Functional studies

Often IEM are rare with only few patients for each gene defect. Moreover, genotype-phenotype correlations can be poor. Therefore, when encountering genetic variants in individual patients, functional studies in (patient) cells can provide crucial evidence for pathogenicity of these variants and thus confirm a molecular diagnosis.

If, with use of the above mentioned techniques, a good candidate gene has been revealed, further alignment with its biochemical and clinical phenotype is necessary. Fibroblast cell cultures, generated from patient skin biopsies, are often used as test material for functional studies for diagnostic purposes. These tests usually focus on the (suspected or known) function of the protein encoded by the gene of interest, and are designed to determine the metabolic and cell biological phenotype of the patient cells. Measurements may consist of (for example) specific enzyme measurements, analysis of metabolic fluxes, or specific metabolite tests. Cultured patient fibroblasts are also desirable for genetic rescue experiments in order to show that the molecular/cellular phenotype observed in the patient fibroblasts can be rescued by introducing the wild type version of the gene, providing further evidence for a role of the gene in the disease of the patient. For some IEM, the affected protein or enzyme might be more apparent in blood cells compared to fibroblasts and therefore various blood cells will be isolated for analysis of the enzymatic activity and protein levels.

Sharing pheno- and genotypic and metabolic data

Due to the rarity of RD phenotypes, elucidation of the genetic disease cause often depends onmatch making in national and international databases . identifying other patients with a similar geno- and/or (metabolic) phenotype. The combination of different patients harboring mutations in the same gene combined with *cell studies* (derived from fibroblast cell lines) or cell models generated by *CRISPR/CAS* technology, can be used to show the specific effect of the mutation on protein function and phenotype (Chatzisprou et al., 2015; van der Crabben et al., 2016; Rumping et al., 2018; Tessadori et al., 2018).

Standardized collection and labelling of patient data enables sharing data with cooperation partners. Moreover, after identification of a candidate gene and functional studies, multiple unrelated patients with mutations in the same gene are needed to establish phenotypical width of a (new) genetic disorder. Moreover, data sharing speeds up the diagnostic process diagnosis.

This study: implementing new diagnostic technologies in undiagnosed patients

The benefit of combining (deep) exome/genome sequencing, RNA sequencing and “omics” technologies, followed by functional studies to diagnose a single or a small group of patient(s), has convincingly been demonstrated. However, this approach is not standard insurance paid care. In addition, detailed and systematic clinical phenotyping, crucial for future recognition of patients (with late onset disease) has not been implemented in patient care. Based on WES, recent progress of RD gene discovery has been substantial, but peaked in 2012, whereafter both the Online Mendelian Inheritance in Man (OMIM) and Orphanet databases show a decreasing trend in gene discoveries (Boycott et al., 2017). Thus, with the more straightforward RDs having been solved, we must address bottlenecks to maintain, or even accelerate, the current pace of discoveries.

The Amsterdam UMC, Erasmus MC, UMC Groningen, Maastricht UMC, Radboudumc (delegated WGS to commercial facility “BGI Genomics”. After sequencing, WGS data analysis is performed by Radboudumc employed specialists) and UMC Utrecht will combine all necessary expertise and tools to establish exact etiological diagnoses in children and adults. Together we have very experienced pediatric and adult IEM teams consisting of clinicians (pediatricians, internists, neurologists and clinical geneticists) and laboratory specialists (genetic metabolic diseases, molecular geneticists and research groups) that work closely together for deep phenotyping, and integrative genomics and metabolomics. These specialists have united in a consortium, United for Metabolic Diseases (UMD).

We aim to include 500 undiagnosed patients suspected of having and IEM from all six clinical centers. The study will last at least 5 years; we expect to enrol on average 100 patients per year. The overall aim of this study is to diagnose patients with an unknown metabolic phenotype. In addition, we want to provide evidence that the combination of approaches and techniques used in this study will increase diagnostic yield compared to current separated approaches. With increasing diagnosis in patients with IEM, more knowledge on natural disease history and pathophysiological background will be gained, paving way for future therapeutics. In addition, families can receive proper counselling and will have options for reproductive choices.

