2. OBJECTIVES

Primary Objective

With this study, in patients with an unknown metabolic phenotype, we want to identify the genetic cause and align it with its biochemical and phenotypical abnormalities. Moreover, with joined forces of the UMD we would like to pave way for implementation of these extended genetic and omics techniques in clinical care. Only with a solid genetic diagnosis patients will be able to receive (future) treatment, prognostication and patient's families can receive proper counselling, including reproductive options.

Secondary Objective(s):

- 1) identification and validation of novel, IEM related, genes/phenotypes/pathways
- 2) to study how omics and genomics complement each other in diagnosing rare disease (genetic cause, biomarker, pathophysiology, natural disease history)

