8.1.3 Other study parameters

[figure not shown]
Evaluation of the yield of the diagnostic approach used in the study. Yield of integrated analysis of the –omics datasets and whole exome/whole genome sequencing dataset for validation of causality of the identified variants.

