10. STATISTICAL ANALYSIS

The only statistics will be a descriptive analysis on the number of patients included. We will also report the number of patients with a confirmed diagnosis and the average time to diagnosis.

10.1

Not applicable

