10.3 Secondary study parameter(s)

Not applicable

10.4

Not applicable

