10.5 Other study parameters

Not applicable

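### Section 10's closed list of statistics gives an overall yield but nothing on what combining or integrating the techniques added

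*Protocol*

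**What the plan says.** Three places ask for more than a total count of diagnoses.

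- Section 1 (closing part, on this study) adds to the aim of diagnosing patients that the study should "provide evidence that the combination of approaches and techniques used in this study will increase diagnostic yield compared to current separated approaches".
- Section 2, secondary objective 2, is "to study how omics and genomics complement each other in diagnosing rare disease (genetic cause, biomarker, pathophysiology, natural disease history").
- Section 8.1.3 lists two parameters. The first is the yield of the study's diagnostic approach as a whole. The second is "Yield of integrated analysis of the –omics datasets and whole exome/whole genome sequencing dataset for validation of causality of the identified variants".

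Section 10 states: "The only statistics will be a descriptive analysis on the number of patients included". It continues: "We will also report the number of patients with a confirmed diagnosis and the average time to diagnosis". Nothing is broken down by technique, step or type of evidence. The entries for the primary, secondary and other parameters (10.2, 10.3, 10.5) are each marked not applicable.

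In section 8.3, WES reanalysis, WGS and metabolomics all belong to Step I. Deep WES, lipidomics and glycomics follow in Step IIB if Step I gives no diagnosis. Step IIA, for patients with a candidate variant, adds repeat metabolomics, RNA analysis, functional studies, segregation analysis and data sharing.

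**The concern.** A total yield counts every diagnosis alike. One reached by rereading an old exome against newer databases weighs the same as one that could be confirmed only because metabolomics or a functional assay supported the variant. All patients enter undiagnosed, and section 4.2 accepts an earlier gene panel as well as an open exome, so wider sequencing or the passage of time could by itself produce diagnoses.

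The primary objective also speaks of bringing the extended genetic and omics techniques into clinical care. For that purpose it matters whether omics or functional data were needed. If section 10 is followed as written, the final report will give one proportion and one mean time, and no planned figure on this question.

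**Working it through.** **1. Reproducing the plan's own figures (section 4.4).** Inputs: N = 500; expected yield 33%, with 34% in the cited programme; novel candidate gene in 1 of 25.

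- 500 × 0.33 = 165; 500 × 0.34 = 170, the stated count.
- 500 / 25 = 20, the stated number of novel genes.
- Exact (Clopper-Pearson) 95% CIs: 165/500 = 33.0% (28.9% to 37.3%); 170/500 = 34.0% (29.9% to 38.3%).

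**2. Aims set against the listed statistics.**

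- Primary aim, main endpoint 2 in the Summary, and first sentence of 8.1.3: served by diagnosed/included.
- Gain after inconclusive standard care: also served, because inclusion requires that standard work-up has failed.
- Second sentence of 8.1.3 (integrated analysis): not served, since no listed statistic separates integrated from non-integrated diagnoses.
- Secondary objective 2: the biomarker, pathophysiology and natural-history parts can be narrative; the diagnostic part has no statistic.
- Section 1 statement on the combination: served only as a gain over prior care.

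**3. What the protocol's quoted rates allow.** Section 1 quotes 10% for reanalysis (40 exomes; 4/40, exact CI 2.8% to 23.7%), 15 to 40% for WGS, and 10-35% for RNA sequencing after failed WES. These come from other cohorts. Applying the WGS rate after reanalysis is an assumption, because the protocol does not say how they overlap.

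- Reanalysis: 0.10 × 500 = 50, leaving 450.
- WGS read as a range: 0.15 × 450 = 67.5 to 0.40 × 450 = 180. Sequencing total: about 118 to 230.
- Left for omics or functional data: 165 − 118 = 47 down to 0, or 170 − 118 = 52 down to 0.
- WGS read as a rise from 15% to 40% (25 points): 0.25 × 450 = 112.5, total about 163, leaving 2 of 165 or 7 of 170.
- RNA sequencing: 0.10 × 500 = 50 to 0.35 × 500 = 175, although 8.3 runs it only in patients with a candidate variant.

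So the same total fits an omics contribution of nothing or of a substantial share.

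**4. Would counts by step do?** In part. A Step IIA exit indicates that confirmatory work was done, which informs the causality-validation yield. But segregation analysis and data sharing also sit in Step IIA, so the count does not say which evidence decided. For Step I exits a count by step gives no separation, because reanalysis, WGS and metabolomics all sit there.

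**5. Precision if attribution were recorded.** Illustrative exact 95% CIs: 0/500 = 0% (0 to 0.7%); 25/500 = 5.0% (3.3% to 7.3%); 50/500 = 10.0% (7.5% to 13.0%). An added yield between 0% and 10% would be known to within about 3 percentage points.

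**The case against.** The strongest reply concerns the comparator. Section 1 describes current practice with the words "Commonly, there are 2 main diagnostic trajectories that can be applied": targeted metabolic screening, and genetic testing. Reanalysis and WGS appear in the later list of new possibilities, so they belong to the study's package and not to current care. On that reading diagnosed/included is the gain over separated approaches, and the sentence in section 1 does not require omics to have been decisive. This stands. It would be wrong to infer that the overall yield says nothing about a gain over current care. What remains is that the figure cannot separate combining from simply adding tests, which is what the second sentence of 8.1.3 and secondary objective 2 ask about.

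A reader might also infer from the quoted rates that sequencing alone would reach 33%. The documents do not support this. The WGS figure is a combined diagnostic and discovery yield from other cohorts, whereas the endpoint in 8.1.1 requires ACMG class IV or V and established causality.

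Finally, a breakdown of this kind often sits in an SAP, and neither an SAP nor Figure 1 was available for this review. An attribution rule could exist there. But the protocol is not silent: it uses the word only, and it marks 10.5 not applicable although 8.1.3 defines other parameters. An SAP that added the table would depart from section 10. The loose wording of section 10, whose second sentence extends the first, does not bring in a breakdown either.

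**Conclusion.** The point holds in a limited form. The planned statistics serve the primary aim and give the yield after inconclusive standard care, expected at 33% to 34% with an interval of about 29% to 38%. They leave the second sentence of 8.1.3 and the diagnostic part of secondary objective 2 without a statistic, and they support the section 1 statement only as a gain over prior care.

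The size of the gap is the whole split between sequencing and omics. The calculation from the quoted rates leaves 0 to 52 diagnoses to omics or functional data. That range rests on transported rates and an assumed overlap, and shows only that the split is unknown. The conclusion itself does not depend on those rates: it follows from setting section 10 beside sections 1, 2 and 8.1.3. It should be fixed, but it does not threaten the primary aim.

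**What to change.** 1. **Record attribution on the CRF.** Before integration at the ZOEMBA diagnostic meeting, enter the candidate variants with ACMG class from WES reanalysis and from WGS, and the metabolomics result (abnormal or not, pathway indicated). After integration, enter which evidence was needed to reach class IV or V, and whether omics led to the variant being prioritised. Recording before the meeting limits hindsight.
2. **Replace the closed list in section 10 and the entry in 10.5** with one descriptive table with exact 95% CIs, counting each patient once.
   - By exit step: Step I, IIB, IIA (direct or via IIB), matchmaking.
   - By decisive evidence: sequencing alone (reanalysis, WGS or, where done, deep WES); sequencing with the variant prioritised by omics; class IV or V reached only with omics, RNA or functional data. State that trio and segregation data count as sequencing evidence.
   - Do not rank deep WES ahead of Step I metabolomics. Deep WES is done only after Step I fails, so its result is unknown for Step I exits. The middle category is needed because a strict sequencing-first order would hide cases where metabolomics pointed to a variant already on the list.
   - Give both number tested and number included as denominators, since patients diagnosed in Step I leave the study. Present the result as an estimate, not a test.
3. **Reword the section 1 sentence** as estimating the yield added after inconclusive standard care, or name the comparator.

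Cost: a few CRF fields, some recording before each meeting (the reanalysis variant list is already drawn up for discussion), and a short rewrite of section 10. Some cells will be small, and a smaller yield may be credited to omics. The difference between the Summary and 8.3 on the step in which WGS is done is a separate editorial point.
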